9.2.4. Endpoints Related to Pharmacokinetics of Ertugliflozin

Details on the pharmacokinetic analysis may be found in the Statistical Analysis Plan. The pharmacokinetic data from this trial may be combined with data from other studies for population pharmacokinetic analysis using nonlinear mixed effects modeling. If data permit, estimates of population pharmacokinetic parameters such as CL/F as well as estimates of inter-individual and residual variability will be determined. In addition, effects of demographic or physiologic factors (eg, age, race, weight, gender, renal function) on pharmacokinetic parameters will be assessed. The results will be summarized in a separate report.

9.3. Safety Analysis

The safety analysis population will consist of all treated subjects, ie, all subjects who received at least one dose of investigational product.

The Medical Dictionary for Regulatory Activities (MedDRA) will be used to classify all adverse events (AEs) with respect to system organ class and preferred term. Summaries of AEs will include treatment-emergent AEs according to treatment group.

To avoid the confounding influence of rescue therapy, the primary approach for most safety analyses will exclude data from the period following the initiation of rescue therapy. A secondary approach will include data following the initiation of rescue therapy. For serious AEs and discontinuations due to AEs, the approach that includes data following the initiation of rescue therapy will be considered primary.

Descriptive statistics will be used to summarize results and changes from baseline in clinical laboratory tests and in vital signs. The number and percentage of subjects with abnormal findings from ECGs will be tabulated by treatment group.

Furthermore, a 3-tier approach will be used to summarize AEs. Tier-1 consists of pre-specified adverse events of interest, and will include AEs or collections of AEs related to urinary tract infection, genital mycotic infection, hypoglycemia and hypovolemia. Where available, standard MedDRA queries will be used to pool different AE terms that are related to the Tier-1 AEs. The precise AE terms that will contribute to the Tier-1 endpoints will be

090177e1848ce2dd\Approved\Approved On: 23-Sep-2013 15:48

determined prior to unblinding. For these events, the percentage of subjects with incident AE, the risk difference, its 95% confidence interval, and p-value will be provided. The confidence intervals and p-values are not adjusted for multiplicity and are provided for screening purposes only. Tier-2 AEs are those that are not Tier-1, but are common, occurring in at least 4 subjects in any treatment arm. The cut-off of at least 4 events was chosen because the 95% confidence interval for the between-group difference in percent incidence will always include zero when treatment groups of equal size each have less than 4 events and so adds little to the interpretation of potentially meaningful differences. For these events, the percentage of subjects with incident AE, the risk difference and its 95% confidence interval will be provided. The confidence intervals are for estimation purposes only. Tier-3 AEs are all other AEs (neither Tier-1 nor Tier-2). For Tier-3 AEs, only within-group incidence proportions will be tabulated.

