1.4. Safety Information for Ertugliflozin and Other SGLT2 Inhibitors

Several SGLT2 inhibitors are in clinical development and as of August 2013, one SGLT2 inhibitor is approved in the U.S. (canagliflozin) and another (dapagliflozin) is approved in the European Union. Based on available clinical trial data with dapagliflozin and canagliflozin, several potential risks from SGLT2 inhibition have been identified. In clinical trials, the rate of genital fungal infections in males and females has consistently been higher in subjects receiving SGLT2 inhibitors as compared to placebo or other diabetes medications. Therefore, the increased risk of genital fungal infections can be considered a class effect of SGLT2 inhibitors. Glucosuria can potentially result in increased risk of urinary tract infection (UTI). In some clinical trials with SGLT2 inhibitors, the reported rate of UTI was slightly higher in subjects treated with an SGLT2 inhibitor compared to those receiving placebo.

SGLT2 inhibition leads to an increase in urinary excretion of glucose and sodium, a diuretic effect and a decrease in blood pressure similar to that reported with other agents with a diuretic action. In clinical trials with other SGLT2 inhibitors, this diuretic effect led to a higher frequency of adverse events such as pollakiuria, thirst and polyuria, but these events were typically of mild severity and usually did not lead to discontinuation. However, certain

populations of subjects (eg, elderly or renal insufficient) may be at risk for hypovolemia-related adverse events from this mechanism. As SGLT2 inhibition can lead to volume depletion, there is also a potential concern for decreased estimated glomerular filtration rate (eGFR) on a hemodynamic basis. In subjects with moderate renal impairment, there was a slightly higher incidence of renal-related adverse events reported in subjects receiving SGLT2 inhibitors than controls in clinical trials with other SGLT2 inhibitors. Small initial decreases in the estimated glomerular filtration rate (eGFR) were seen, which returned toward baseline levels over time with continued treatment and/or upon discontinuation of therapy, consistent with a reduction in plasma volume. The reversibility with continued treatment or with discontinuation of treatment is consistent with a hemodynamic (plasma volume) mechanism.

Routine safety monitoring for these adverse events will be performed in this study.

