6.7.2.1. Follow-up for Subjects who Discontinue Due to Decreased Renal Function

Subjects who discontinue blinded investigational product for eGFR/creatinine discontinuation criteria (see [Section 6.7.2](#)) or renal-related adverse events should have a repeat eGFR/creatinine performed 1 week after the last dose of Investigational Product. This post-treatment visit may occur at the Discontinuation visit (if the Discontinuation visit occurs 1 week after the last dose of Investigational Product) or at an unscheduled visit. The out of range test(s) should continue to be repeated at intervals, as considered appropriate (eg, weekly or every other week) until the value returns to baseline (pre-randomization value) or a new baseline is established. The Investigator should implement an appropriate evaluation for events of clinically significant change in eGFR (eg, >30% reductions in eGFR from baseline values). Such an evaluation should include detailed review of any associated symptoms, thorough review of concomitant medications (including “over the counter” agents) to determine if the subject had any change (new initiation or change in dose) in his or her medication regimen with agents associated with decreases in eGFR (eg, non-steroidal anti-inflammatory agents, fenofibrate, angiotensin-converting enzyme (ACE) inhibitors, diuretic agents, etc), and clinical assessment of volume status (eg, measurement of orthostatic heart rate [HR] and blood pressure [BP], and physical examination focused on assessment of volume status); additional evaluations, including renal ultrasound, and microscopic urinalysis (with culture and sensitivity if infection is considered possible), urine creatinine and electrolytes, should be performed, as clinically appropriate.

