7.4.3. Postural (Orthostatic) Blood Pressure and Pulse Rate

On the S3, Day 1, Week 6 and Week 26 visits, duplicate measurements of supine and standing blood pressure and pulse rate will be taken in order to evaluate postural changes in blood pressure and pulse rate. These measurements will be in addition to the sitting blood pressure and pulse rate measurements taken on these clinic visits (except for S3 visit).

Measurement of postural blood pressure and pulse rate will also occur at the glycemic Rescue Visit.

Postural blood pressure changes will be measured according to the following procedure:

- Subject in supine position for a minimum of 5 minutes.
- Measure blood pressure and pulse rate in the supine position in duplicate (at least 1 minute apart).
- Stand subject and measure blood pressure and pulse rate in the standing position in duplicate according to the following instructions. The first measurement of standing blood pressure and pulse rate will be measured after at least 1 minute of standing. The second measurement of standing blood pressure and pulse rate will be measured after the subject has been standing for at least 3 minutes.

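### Section 9.3 pre-specifies no by-arm count of subjects with a marked eGFR or creatinine change or an orthostatic drop, although both are measured for named class risks

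*Combined protocol and SAP*

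**What the plan says.** Section 1.4 names both risks. On the kidney, "there is also a potential concern for decreased estimated glomerular filtration rate (eGFR) on a hemodynamic basis". On volume, certain populations "may be at risk for hypovolemia-related adverse events from this mechanism".

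The measurements are scheduled. Serum creatinine is in the chemistry panel (Section 7.4.1, Table 5), which is drawn at most visits. Under Section 7.4.3, supine and standing readings are taken at S3, Day 1, Week 6, Week 26 and the rescue visit, "in order to evaluate postural changes in blood pressure and pulse rate".

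Individual renal limits exist for clinical use. Section 6.7.2 stops investigational product for eGFR consistently below 45, or creatinine consistently at or above 1.5 mg/dL (men) or 1.4 mg/dL (women). Section 6.7.2.1 asks the investigator to evaluate "events of clinically significant change in eGFR (eg, >30% reductions in eGFR from baseline values".

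In the analysis, Section 9.3 says "Descriptive statistics will be used to summarize results and changes from baseline in clinical laboratory tests and in vital signs". The next sentence is more specific, but for one data type only: "The number and percentage of subjects with abnormal findings from ECGs will be tabulated by treatment group". The Tier-1 adverse-event topics "will include AEs or collections of AEs related to urinary tract infection, genital mycotic infection, hypoglycemia and hypovolemia"; renal events are not among them. On rescued subjects, "the primary approach for most safety analyses will exclude data from the period following the initiation of rescue therapy", and a secondary approach includes those data.

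**The concern.** Large eGFR falls and orthostatic drops are harms to individuals. If they affect a minority, a summary of level and change by visit is an insensitive way to compare arms, because a few large falls are averaged with many small changes. The protocol already treats particular renal values as important enough to evaluate or to stop drug, yet none of those values becomes an analysis category, and no orthostatic category is defined anywhere.

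There is also some selection. A subject stopped under the renal rule has an Early Termination visit and a repeat creatinine one week after the last dose, then by default telephone contact and a Week 104 visit. That subject is mostly absent from the by-visit laboratory summaries in between.

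Safety is a primary objective. A report that follows the text could show a small average change in eGFR and postural pressure without tabulating an excess of subjects with large falls. If a threshold were chosen only after the Phase A results are unblinded (Sections 5.2 and 9.4), it would be post hoc.

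**Working it through.** The plan gives no figure on this point to reproduce. The check is a reading of the text followed by illustrative arithmetic.

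**1. What is counted by arm**

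| Data | Planned summary | Section |
|---|---|---|
| ECG findings | Number and percentage abnormal | 9.3 |
| Hypovolemia AEs | Tier 1: risk difference, 95% CI, p-value | 9.3 |
| Renal AEs | Tier 2 if at least 4 subjects in any arm (risk difference, CI); otherwise Tier 3 (incidence only) | 9.3 |
| Renal failure meeting pre-specified criteria | Blinded external adjudication | 7.8.5 |
| Creatinine, eGFR | Descriptive; no threshold stated | 9.3 |
| Postural blood pressure | Not named; descriptive if it counts as a vital sign | 9.3 |

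Section 7.4.2 uses the term vital signs for sitting measurements, and postural readings have their own Section 7.4.3. It is therefore not explicit that Section 9.3 covers them. The frequency tables in Section 9.2.3.1 apply to categorical endpoints, and no eGFR or orthostatic category is one.

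**2. Reach of the eGFR stopping criterion**

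Entry requires eGFR of at least 55 (Section 4.2).
- From 55, the fall needed to reach 45 is (55 − 45)/55 = 18.2%.
- A 30% fall leaves eGFR at or above 45 when baseline is at least 45/0.70 = 64.3.

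Many subjects with a 30% fall therefore need not stop under the eGFR criterion. They stay in the averages, diluted and uncounted. Those removed by this criterion are mainly subjects with a low baseline.

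**3. Dilution in the mean**

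Assumptions (the documents give none): baseline 75 to 90, SD of change 10 to 15, and an excess fraction of 5% with a 30% fall. There are about 200 subjects per arm (Section 5.1).
- Shift in arm mean = 0.05 × 0.30 × baseline: 1.1 at 75, 1.4 at 90.
- 95% half-width of the difference = 1.96 × SD × √(2/200): 2.0 at SD 10, 2.9 at SD 15.

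**4. Mean and count on the same assumed data**

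Assume a 30-unit fall in 6% versus 2%, all retained, 200 per arm.
- Mean difference moves by 30 × (0.06 − 0.02) = 1.2 units. SE = SD × √(2/200) = 1.00, 1.20, 1.50 for SD 10, 12, 15. With 170 per arm it is 1.08, 1.30, 1.63.
- Counts of 12/200 versus 4/200 give a risk difference of 4.0%, Miettinen-Nurminen 95% CI 0.2% to 8.4%. Fisher's exact p is 0.07.
- One event fewer (11/200 versus 4/200) gives a 95% CI of −0.3% to 7.8%.

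**5. What a count can detect at 200 per arm** (assumed rates, two-sided 0.05)

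| Control | Ertugliflozin | Difference | 95% half-width (Wald) | Power |
|---|---|---|---|---|
| 1% | 3% | 2.0 points | 2.7 | 30% |
| 1% | 5% | 4.0 points | 3.3 | 65% |
| 1% | 8% | 7.0 points | 4.0 | 93% |
| 5% | 10% | 5.0 points | 5.1 | 48% |

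The count is the more sensitive summary in these examples, but it is not a powerful test for small excesses.

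**The case against.** Much of the safety plan already addresses these risks. Hypovolemia, which Section 1.4 frames in terms of adverse events, is Tier 1 with a formal contrast. Abnormal laboratory findings can be reported as adverse events. Discontinuations due to adverse events are analysed with post-rescue data included as the primary approach. Renal failure is adjudicated, and an external committee reviews unblinded safety data. Descriptive statistics can include counts, and Section 9 defers detail to a separate SAP whose text is not in the document reviewed. All of this stands. It limits the point to what the protocol pre-specifies; it does not supply a count of measured falls, because adverse-event reporting depends on the investigator's judgement and adjudication covers renal failure only.

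A reader might infer that these harms are never counted by arm. The documents do not support that, for the reasons just given.

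A reader might also infer that affected subjects drop out of the averages, so that the results are biased towards reassurance. That goes too far:
- No stopping rule refers to an orthostatic drop.
- eGFR falls that stay above the stopping limit do not remove a subject by that criterion.
- Subjects who stop have chemistry at the Early Termination visit, a repeat at one week, further repeats at intervals while out of range, and a Week 104 visit. Section 6.7 also allows continued clinic visits.
- Rescue is triggered by glucose or HbA1c, nothing links rescued subjects to the worst renal courses, and the secondary approach includes post-rescue data.

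Finally, the 30% figure is an example in investigator guidance, and the stopping limits require a repeat value. They are usable as tabulation categories but are not analysis definitions that the protocol has adopted.

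**Conclusion.** The point holds in a limited form. Section 9.3 pre-specifies no threshold-based, by-arm count for measured eGFR, creatinine or postural change, although the protocol names the risks, collects the data, holds individual renal limits and counts abnormal ECGs. The main mechanism is dilution. Selection is a second, narrower one, confined to subjects stopped under the renal rule and, in the primary approach only, to post-rescue values.

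The size cannot be fixed from the documents. The event rates, baseline eGFR, SD and size of fall above are all assumptions. On them, a mean shift of 1.1 to 1.4 units sits inside a half-width of 2.0 to 2.9, whereas a 4-point excess in counts is at the edge of detection. The gain is real but modest. The change is worth making because safety is a primary objective and the cost is small; the efficacy conclusions are unaffected.

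**What to change.** Before Phase A unblinding, add to Section 9.3 (and carry into the SAP), for Phase A and for Weeks 0 to 104:

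- The number and percentage of subjects by arm, with risk difference and 95% CI versus control, who have any post-baseline value (scheduled, unscheduled, rescue or Early Termination) in each category: eGFR fall greater than 30% from baseline; eGFR below 45; creatinine at or above 1.5 mg/dL (men) or 1.4 mg/dL (women). Show confirmed values, using the repeat-measurement definition in Section 6.7.2, alongside. These serve as tabulation categories only and change no clinical rule.
- The same for orthostatic drop at Week 6, Week 26 and any Phase A visit, with one cut-off that the sponsor chooses and justifies in advance.
- A statement that vital signs in Section 9.3 include postural blood pressure.

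The postural data definition also needs reconciling. Section 6.3.5 calls for triplicate orthostatic readings at Week 26, while Section 7.4.3 and the Schedule of Activities say duplicate. Section 7.4.3 also omits the Phase A restriction on rescue-visit readings given in Section 6.6 and the Schedule.

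The cost is SAP wording and two or three tables from data already collected, with no new procedure. The downsides are a few more intervals without multiplicity adjustment, and any-value counts that include transient falls, which is why confirmed values should sit beside them.

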6.1.1. Dispense Hypoglycemia Assessment Log and Instruct on Hypoglycemia Symptoms and Management

At S2, the site will review the symptoms and management of hypoglycemia with the subject. The site will counsel the subject to perform a fingerstick glucose measurement if any symptoms occur that may be related to hypoglycemia (eg, weakness, dizziness, shakiness, increased sweating, palpitation, or confusion), but also to avoid delay in treating these symptoms.

The subject will be instructed to complete the Hypoglycemia Assessment Log for any symptomatic episodes he or she believes may represent hypoglycemia. If a fingerstick glucose has been obtained before or shortly (ie, within a few minutes) after treating, the value should be recorded in the log. In addition, subjects will be instructed to record in the log any fingerstick glucose values ≤ 70 mg/dL (3.9 mmol/L) regardless of the presence of clinical symptoms.

Subjects should be instructed to contact the investigational site to report:

- Any episode of hypoglycemia for which assistance was required (ie, severe hypoglycemia).
- Any episode of fingerstick glucose ≤ 70 mg/dL (3.9 mmol/L) with or without symptoms.

Note: As indicated, subjects will record symptoms and/or fingerstick glucose measurements that they believe are related to hypoglycemia on the log. Each episode should be evaluated by the Investigator. For episodes determined to be hypoglycemia (symptomatic or

asymptomatic), and for all glucose values ≤ 70 mg/dL (3.9 mmol/L) regardless of whether they are considered an adverse event, the hypoglycemia assessment (HA) electronic case report form (eCRF) must also be completed. Each event of symptomatic hypoglycemia must be reported as an adverse event on the adverse event eCRF. Each episode of asymptomatic hypoglycemia considered by the Investigator to be an adverse event should also be reported on the adverse event eCRF.

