7.4.6.1. Management of Hypoglycemia

Subjects will be instructed to check fingerstick glucose when they have symptoms consistent with hypoglycemia such as hunger, headache, dizziness, light headedness, sweating, palpitation, tachycardia, tremulousness, irritability, blurred vision, and disorientation. Subjects should be instructed to call the site should these symptoms occur and/or worsen before next visit.

A subject should be discontinued from the investigational product if they have repeated (2 or more episodes since the prior visit) FPG or fingerstick glucose <50 mg/dL (<2.8 mmol/L) with or without symptoms of hypoglycemia or ≤ 70 mg/dL (≤ 3.9 mmol/L) with symptoms of hypoglycemia, and without a reasonable explanation (such as increased physical activity or skipped meal).

Any episode of hypoglycemia must be captured on the Hypoglycemic Adverse Event Form of the CRF (refer to [Section 6.1.1](#)). For definition of hypoglycemic episode and severity categorization, refer to Section 7.4.6.1.1 below.

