7.4.6.1.1. Definition and Severity Categorization of Hypoglycemic Events

Based on review of the subject completed hypoglycemia assessment logs at each outpatient visit to the site, the Investigator must assess the glucose values as well as any symptoms documented. Each hypoglycemic event will be reported by the Sponsor according to the following categories.

Severe Hypoglycemia: An event requiring assistance of another person to actively administer carbohydrate, glucagon, or other resuscitative actions. These episodes may be associated with sufficient neuroglycopenia to induce seizure or coma. Finger-stick or plasma glucose measurements may not be available during such an event, but neurological recovery attributable to the restoration of plasma glucose to normal is considered sufficient evidence that the event was induced by a low plasma glucose concentration.

Documented Symptomatic Hypoglycemia: An event during which typical symptoms of hypoglycemia are accompanied by a measured finger-stick or plasma glucose concentration ≤ 70 mg/dL (3.9 mmol/L).

Asymptomatic Hypoglycemia: An event not accompanied by typical symptoms of hypoglycemia but with a measured finger-stick or plasma glucose concentration ≤ 70 mg/dL (3.9 mmol/L).

Probable Symptomatic Hypoglycemia: An event during which symptoms of hypoglycemia are not accompanied by a fingerstick or plasma glucose determination, but was presumably caused by a plasma glucose concentration ≤ 70 mg/dL (3.9 mmol/L). Since many people with diabetes choose to treat symptoms with oral carbohydrate without a test of plasma glucose, it is important to recognize these events as probable hypoglycemia.

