7.4.6.1.2. Guidance on Adverse Events Related to Hypoglycemia

All episodes considered as likely to represent symptomatic hypoglycemia by the Investigator must be captured as an adverse event of "symptomatic hypoglycemia." This diagnosis may be supported by, but does not require, confirmatory blood glucose results (such as those measured using a fingerstick or from a clinical laboratory sample). Further, at the discretion of the Investigator, an asymptomatic finger-stick or plasma glucose value ≤ 70 mg/dL (3.9 mmol/L) from either a fingerstick or central laboratory sample may be reported as an adverse event of "asymptomatic hypoglycemia." General guidance regarding the determination as to whether an event is considered to be an adverse event should be followed (see [Section 8.1](#)).

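### The only hypoglycemia comparison between arms in Section 9.3 is a count of AE terms; the categories of Section 7.4.6.1.1 should get an estimate beside it

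*Combined protocol and SAP*

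**What the plan says.** Section 9.3 (Safety Analysis) sorts adverse events into three tiers. Tier-1 "will include AEs or collections of AEs related to urinary tract infection, genital mycotic infection, hypoglycemia and hypovolemia". The terms are grouped by MedDRA query where one exists, and the precise list is fixed before unblinding. For Tier-1 items, "the percentage of subjects with incident AE, the risk difference, its 95% confidence interval, and p-value will be provided". The plan limits their standing: "The confidence intervals and p-values are not adjusted for multiplicity and are provided for screening purposes only".

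Whether an episode becomes an AE is settled elsewhere:

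- **Symptomatic episodes.** Section 7.4.6.1.2 requires an AE whenever the investigator judges symptomatic hypoglycemia likely. On glucose it says: "This diagnosis may be supported by, but does not require, confirmatory blood glucose results".
- **Asymptomatic values of 70 mg/dL or less.** Section 7.4.6.1.2 leaves AE entry to the investigator's discretion. Section 6.1.1 agrees: "Each episode of asymptomatic hypoglycemia considered by the Investigator to be an adverse event should also be reported on the adverse event eCRF".

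Section 6.1.1 also requires the hypoglycemia assessment (HA) eCRF for every value of 70 mg/dL or less, AE or not, and for every episode determined to be hypoglycemia.

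Section 7.4.6.1.1 defines severe, documented symptomatic, asymptomatic and probable symptomatic hypoglycemia, and states: "Each hypoglycemic event will be reported by the Sponsor according to the following categories". Section 9.3 does not refer to these categories. Section 7.4.6.1 says: "Any episode of hypoglycemia must be captured on the Hypoglycemic Adverse Event Form of the CRF", with a cross-reference to Section 6.1.1, which treats the HA eCRF and the AE eCRF as separate forms.

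**The concern.** Hypoglycemia is one of four pre-specified events of interest. Its between-arm estimate rests on whether an AE was entered, and for asymptomatic low values the protocol leaves that open. Two sites that both follow the protocol can handle the same record differently. One enters a fingerstick of 60 mg/dL without symptoms as an AE; the other records it only on the HA eCRF.

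The trial therefore collects every recorded value of 70 mg/dL or less under one rule, but compares the arms on a count that partly follows reporting habit. That count also need not match the category counts the sponsor will report, and a reader who wants those categories compared between arms has no pre-specified estimate. The question is sharper in Phase B, where placebo subjects not rescued in Phase A may start blinded glimepiride (Section 5.3.5), a drug whose initiation the protocol itself links to hypoglycemia risk.

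**Working it through.** **Step 1: how each kind of episode is handled.**

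| Episode | Entered as AE? (6.1.1, 7.4.6.1.2) | Category (7.4.6.1.1) | Measured value of 70 mg/dL or less needed for category? |
|---|---|---|---|
| Symptoms, glucose 62 | Yes, if judged likely | Documented symptomatic | Yes |
| No symptoms, glucose 60 | Investigator's discretion | Asymptomatic | Yes |
| Symptoms, no measurement | Yes, if judged likely | Probable symptomatic | No |
| Symptoms, glucose 95, judged likely | Yes | None, unless severe | – |
| Assistance needed | Yes if symptomatic hypoglycemia is judged likely | Severe | No |

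The glucose values are hypothetical. The second row carries the point: entry is discretionary. The third row is consistent with the protocol's own definitions. The fourth shows that the AE count and the category counts can differ.

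**Step 2: is there another between-arm estimate?** The 12-step hierarchy in Section 9.2.2 contains no hypoglycemia endpoint. Laboratory results are summarized descriptively (Section 9.3). An asymptomatic hypoglycemia AE term left out of Tier-1 would fall under the Tier-2 or Tier-3 rules, which still count AEs. Section 9 defers detail to a separate SAP whose text is not available here, so the answer is none in this text.

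**Step 3: can the size be worked out?** There is no hypoglycemia figure in the plan to reproduce. Only the arm size (200, Section 9.1) is from the documents; every rate below is assumed. Wald half-width = 1.96 × √[p1(1−p1)/200 + p0(1−p0)/200].

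*A. Extra discretionary or unconfirmed AEs at the same rate k in both arms*, on top of 3% v 1%. Per arm, p = 1 − (1 − true rate)(1 − k).

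| k | p1 v p0 | Difference ± half-width (points) | Risk ratio |
|---|---|---|---|
| 0 | 3.00% v 1.00% | 2.00 ± 2.74 | 3.00 |
| 2% | 4.94% v 2.98% | 1.96 ± 3.82 | 1.66 |
| 4% | 6.88% v 4.96% | 1.92 ± 4.62 | 1.39 |
| 6% | 8.82% v 6.94% | 1.88 ± 5.28 | 1.27 |

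Starting from 5% v 2%, the half-width goes from 3.59 to 4.43, 5.11 and 5.68 points.

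*B. Asymptomatic values that differ by arm.* Symptomatic AEs 5% v 3%, asymptomatic values 10% v 5%, fraction f of the latter entered as AEs. p1 = 0.05 + 0.95 × 0.10f; p0 = 0.03 + 0.97 × 0.05f.

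| f | p1 v p0 | Difference ± half-width (points) |
|---|---|---|
| 0 | 5.0% v 3.0% | 2.0 ± 3.8 |
| 0.5 | 9.75% v 5.43% | 4.3 ± 5.2 |
| 1 | 14.5% v 7.85% | 6.65 ± 6.1 |

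*C. Extra AEs in the same 3:1 ratio as the true events*: 6% v 2% added to 3% v 1%. p1 = 1 − 0.97 × 0.94 = 8.82%; p0 = 1 − 0.99 × 0.98 = 2.98%. The difference is 5.84 ± 4.58 points, an interval of 1.3 to 10.4.

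In A the added AEs only cost precision. In B and C the broader count shows a larger difference, and at f = 1 in B and in C the interval excludes zero. The assumed rates decide the direction.

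**The case against.** A reader might infer that the AE-based count dilutes the comparison and hides a real excess, so that a glucose-confirmed endpoint should replace it. The documents do not support that.

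- **Direction.** Nothing in the documents says discretionary events occur equally in all arms. Scenario A assumes it; B and C reverse the result. Even in A, the difference, which is the plan's measure, barely moves (2.00 to 1.88 points), and the interval already includes zero with no extra events (2.00 ± 2.74).
- **The categories are not all glucose-based.** Severe and probable symptomatic episodes need no value, and Section 7.4.6.1.1 stresses recognizing the latter. A glucose-confirmed replacement would drop probable symptomatic episodes from the comparison.
- **Term selection helps.** Section 7.4.6.1.2 names separate symptomatic and asymptomatic AE terms. Fixing the terms before unblinding can remove the asymptomatic discretion, provided coding keeps the two apart.
- **Standing and blinding.** The p-value is for screening, the categories will still be reported, and Phase A is blinded to subject, investigator and sponsor (Section 5.2), so known allocation should not steer AE entry.
- **The alternative also has discretion.** The investigator sets each subject's home monitoring frequency (Section 6.1) and assesses symptoms.

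All of this stands, and it rules out calling the Tier-1 analysis wrong. It leaves one gap: the plan does not say whether asymptomatic AEs are in the count, and it specifies no between-arm estimate that is independent of AE entry.

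**Conclusion.** The point holds in a limited form. In the available text, the only hypoglycemia comparison with a between-arm estimate is a screening-level count of AE terms. Asymptomatic values of 70 mg/dL or less enter it at the investigator's discretion, and the Section 7.4.6.1.1 categories have no specified comparison. The size and direction of any effect on the result are unknown; the scenarios show only that reporting practice can matter under some assumed rates. The word only is conditional on the separate SAP, which may already supply the comparison. The form name in Section 7.4.6.1 is an editorial mismatch: its cross-reference leads to Section 6.1.1, and it does not override the discretion rule. Priority: consider; a cheap improvement.

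**What to change.** Keep the Tier-1 AE analysis. Before unblinding, state in Section 9.3 or the SAP whether asymptomatic hypoglycemia AEs are included in it. Beside it, add subject incidence, risk difference and 95% CI, derived from the HA eCRF, for:

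- (a) documented symptomatic (70 mg/dL or less with symptoms) or severe hypoglycemia;
- (b) any documented value of 70 mg/dL or less, with or without symptoms.

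Show probable symptomatic episodes as a separate row, so that they stay visible. Reconcile the form name in Section 7.4.6.1 with Section 6.1.1.

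The cost is a short paragraph, a few table rows and a form-name correction; no new data are needed. Row (b) will still depend on how often each subject self-monitors, and the table should say so.
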